## 5. STUDY DESIGN

This is an open-label, non-randomized Phase I/II study of patients with relapsed or refractory multiple myeloma.

The Phase I study will determine the MTD of the combination of carfilzomib and panobinostat. The Phase I portion will follow a standard dose escalation design, beginning with dose level 1 (see Table 2). Patients will be assessed for dose-limiting toxicity (DLT) at each visit during Cycle 1 prior to receiving treatment. Dose modifications will not be permitted during Cycle 1 unless a patient experiences a DLT (see Section 5.2.2.). Treatment cycles will be administered at 28-day intervals. Panobinostat will be administered orally three times weekly during weeks 1 and 3 of each cycle (Days 1, 3, 5, 15, 17, 19). Carfilzomib will be administered intravenously on Days 1, 2, 8, 9, 15, and 16 of each cycle. During Cycle 1, the carfilzomib dose will be escalated after the Day 2 dose, if well tolerated.

A maximum of four dose levels were evaluated. No DLTs were seen during the Phase I portion.

In the Phase II portion of this study, patients with relapsed/refractory multiple myeloma will receive treatment with the dose level 4 panobinostat and carfilzomib combination. Patients will be reevaluated for response to treatment after each cycle (4 weeks). Patients with objective response or stable disease will continue treatment, with subsequent reevaluations every 4 weeks, until disease progression or unacceptable toxicity occurs.

[figure not shown]
A parallel Phase I study will occur to evaluate a minimum of 3 patients and a maximum of 6 patients following a standard dose escalation design at additional dose levels of the combination of carfilzomib and panobinostat (see Table 3).

If additional dose levels are found to be tolerable, then additional patients will be recruited into an expansion cohort which will be open at all sites - a maximum total of 36 patients (including the ones recruited into the parallel Phase I study) will be treated at this dose level. Sites will be notified about the expansion cohort and patients will enter in the dose level confirmed in their enrollment confirmation from SCRI Innovations.

Up to 80 eligible patients will be treated in the Phase I/II study. The treatment schema for the study is shown in Figure 2.

Figure 2

Treatment Schema

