### 5.2.2. Definitions of Dose-Limiting Toxicity (DLT)

For the purpose of determining the MTD (see Section 5.2.3), DLT is defined as any of the following that are determined to be related to study treatment during **Cycle 1**:

- Grade 4 neutropenia (absolute neutrophil count [ANC] <500/ $\mu$ L) for >7 days.
- Febrile neutropenia (ANC <1000/ $\mu$ L with fever >101°F [38.5°C]).
- Grade 3 thrombocytopenia with  $\geq$  Grade 2 bleeding.
- Grade 4 thrombocytopenia (platelets <25,000/ $\mu$ L) > 7 days (patients may receive platelet support/transfusion).
- $\geq$  Grade 2 neuropathy with uncontrolled pain
- $\geq$  Grade 3 non-hematologic drug-related toxicity (excluding alopecia) despite optimal supportive care lasting >72 hours or requiring a dose reduction in the first cycle.
- Patients who are unable to receive 75% of the required doses of both agents secondary to toxicity.

Adverse events will be graded using the National Cancer Institute (NCI) Common Toxicity Terminology Criteria for Adverse Events v4.0 (CTCAE v4.0).

Dose modifications are not permitted during Cycle 1 in any cohort unless the subject experiences a DLT. Subjects in dose level -1 (see Table 2) who develop a DLT during Cycle 1 will be discontinued from the study. Subjects in dose level 1 or higher who experience a DLT during Cycle 1 will have treatment held. The DLT will be counted toward the assessment of the MTD for the given cohort; however, the subject may continue on therapy if the toxicity resolves and dose modifications can be implemented according to the dose modification guidelines in Section 6.0.

Patients who withdraw from the study before receiving 75% of their scheduled Cycle 1 doses due a non-drug related AE (i.e., tumor progression) will be considered inevaluable and will be replaced.

Patients without clinical evidence of progressive disease at the end of the first cycle of study therapy will continue treatment. Patients will be reevaluated for response after completing 2 cycles (8 weeks) of treatment. Patients with objective response or stable disease according the International Myeloma Working Group Uniform Response Criteria (see Appendix C) will continue treatment, with reevaluations until disease progression occurs, unacceptable toxicity develops, or the subject chooses to discontinue study treatment.

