**6.1. Dose Modifications for Hematologic Toxicity**

Panobinostat and carfilzomib have been associated with hematologic toxicity. Blood counts will be measured on Days 1, 8, and 15 of each cycle, and dose modifications will be based on these blood counts. Dose reductions, when necessary, are outlined in Table 5. If toxicity occurs when the patient is already on the lowest acceptable dose, the drug should be discontinued.

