**Table 5. Panobinostat and Carfilzomib Dose Adjustments for Hematologic Toxicities**

AE Term and Description	Dose Modification	
	Panobinostat	Carfilzomib
THROMBOCYTOPENIA		
Grade 1 or 2	Maintain dosing; monitor as clinically indicated.	Maintain dosing; monitor as clinically indicated.
Grade 3 (25 - <50 x 10  /L)	
 
1. Interrupt study treatment until toxicity reduced to ≤ grade 2a.
 
2. Restart treatment with a 1 level dose-reduction (Table 3).
 
	
 
1. Interrupt study treatment until toxicity reduced to ≤ grade 2a.
 
2. If improves in ≤ 7 days, maintain same dose, if > 7 days reduce dose 1 level.
 

Grade 4 (<25 x 10  /L)	
 
1. Interrupt study treatment until toxicity reduced to ≤ grade 2a.
 
2. Restart treatment with a 1 level dose-reduction.
 
	
 
1. Interrupt study treatment until toxicity reduced to ≤ grade 2a.
 
2. Restart treatment with a 1 level dose-reduction.
 

Recurrent Grade 3/4 Event After Initial Dose Reduction	
 
1. Interrupt study treatment until toxicity reduced to ≤ grade 2a.
 
2. Restart treatment with a second 1 level dose-reduction.
 
	
 
1. Interrupt study treatment until toxicity reduced to ≤ grade 2a.
 
2. Restart treatment with a second 1 level dose-reduction.
 

Recurrent Grade 3/4 Event After 2 Dose Reductions	Discontinue	Discontinue

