**Table 7: Criteria for Dose Reductions, Delays and/or Re-Institution Due to Drug-Related QTcF Abnormalities**

ECG TIME POINT	ABNORMALITY	DOSE MODIFICATION GUIDELINE
Dose modifications are based on local readings of the average QTcF of triplicate ECGs.		
Cycle 1 Dose Modification Criteria:		
Cycle 1 PRE-DOSE Days 1 and 5 Triplicate ECGs	Day 1: Average QTcF: >450 msec	Check and correct the patient's serum potassium, magnesium, calcium, phosphorus immediately, as well as evaluate concomitant medications. If abnormality noted on Cycle 1 Day 1: Repeat 3 pre-dose ECGs. If the 3 pre-ECGs: Do not meet criteria again, discontinue patient from study. Do meet criteria for dosing; administer panobinostat.
	Day 5: Average QTcF: ≥480 msec to <500 msec Or >60 msec increase from baseline average	If abnormality noted on Cycle 1 Day 5: Delay dose at least 3 days and repeat 3 pre-dose ECGs. If the repeat 3 pre-dose ECGs: Do not meet pre-dose ECG criteria again, discontinue panobinostat. Do meet pre-dose ECG criteria for dosing and QTc prolongation determined to be related to panobinostat, resume panobinostat treatment with a 1-level dose reduction. If however, it was determined that the QTc prolongation was secondary to electrolyte abnormalities or concomitant medications, continue at the same dose level. Repeat ECGs – pre-dose (x3), 3-hours post-dose (x3), on the next scheduled dosing day.
	Average QTcF: ≥500 msec	Check and correct the patient's serum potassium, magnesium, calcium and phosphorus immediately. Discontinue patient from panobinostat.  If however, it was determined that the QTc prolongation was secondary to electrolyte abnormalities or concomitant medications: Omit dose. On the next scheduled dosing day continue at the same dose level. Repeat ECGs - pre-dose (x3), 3-hours post-dose (x3), on the next scheduled dosing day.

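### For dose-finding patients, the ban on Cycle 1 dose changes without a DLT conflicts with the safety reductions in Tables 5–7, and the 75% rule does not resolve it

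*Combined protocol and SAP*

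**What the plan says.** Section 5, in its Phase I paragraph, says: "Dose modifications will not be permitted during Cycle 1 unless a patient experiences a DLT". Section 5.2.2 repeats this for every cohort: "Dose modifications are not permitted during Cycle 1 in any cohort unless the subject experiences a DLT". It brings in Section 6 only after a DLT. Treatment is then held, and the patient may continue if the toxicity resolves and "dose modifications can be implemented according to the dose modification guidelines in Section 6.0".

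Section 6 does not exempt Cycle 1:

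- **Table 7** carries the heading "Cycle 1 Dose Modification Criteria". For QTcF of 480 to below 500 msec, or a rise of more than 60 msec, judged related to panobinostat, it tells the site to "resume panobinostat treatment with a 1-level dose reduction".
- **Section 6.1 and Table 5**: "Blood counts will be measured on Days 1, 8, and 15 of each cycle, and dose modifications will be based on these blood counts". Panobinostat is held and reduced one level for Grade 3 thrombocytopenia or neutropenia. For Grade 4, the instruction for both drugs, once recovered, is "Restart treatment with a 1 level dose-reduction".
- **Table 6** holds and reduces panobinostat for Grade 2 diarrhea or vomiting despite treatment, and for creatinine or bilirubin at 2–3 x ULN.

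The DLT list in Section 5.2.2 is narrower. Thrombocytopenia needs Grade 3 with bleeding, or Grade 4 for more than 7 days. Neutropenia needs fever, or Grade 4 for more than 7 days. General non-hematologic toxicity starts at Grade 3. A last item covers lost doses: "Patients who are unable to receive 75% of the required doses of both agents secondary to toxicity".

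For the parallel study, Table 3 sets level 5 at carfilzomib 56 mg/m² with panobinostat 30 mg, and level 6 at 56 mg/m² with 20 mg. The up-and-down rules in Section 5.2.1 refer only to Table 2.

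**The concern.** The DLT count decides which dose is carried forward, and that is the Phase I primary objective. A dose-finding site that meets one of these events in Cycle 1 has two instructions that cannot both be obeyed.

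If the ban prevails, an ordered safety reduction is withheld. If the tables prevail, a patient on a reduced dose can count as DLT-free at the assigned level. These harms are alternatives, and different sites could choose differently.

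One patient matters in a 3+3 design. Under Section 5.2.1, 0 of 3 escalates while 1 of 3 expands, and 1 of 6 passes while 2 of 6 fails.

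**Working it through.** The plan gives no Cycle 1 dose intensity or reduction rate to reproduce. The check compares the rules and follows patients through them.

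**Inputs.** Table 3: level 5 gives panobinostat 30 mg on Days 1, 3, 5, 15, 17 and 19, and carfilzomib 20 mg/m² on Days 1–2, then 56 mg/m² on Days 8, 9, 15 and 16. Planned Cycle 1 totals are 6×30 = 180 mg and 2×20 + 4×56 = 264 mg/m². One-level steps (Table 4) are panobinostat 30→20→15 mg and carfilzomib 56→45 mg/m². Missed panobinostat is not made up (Section 5.1.1). Labs are repeated weekly until recovery (Table 5 footnote).

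**Case 1, QTcF.** QTcF is 480 to below 500 msec after the Day 1 dose, drug-related, and below 480 msec on Day 3. Table 7 reduces panobinostat from Day 3.
- Panobinostat: (30 + 5×20)/180 = 130/180 = 72%; 6/6 doses taken.
- This is a DLT only if graded 3 or worse. The documents do not grade this trigger.

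**Case 2, Grade 2 diarrhea** despite loperamide, starting after the Day 3 dose. Day 5 is omitted, it settles by Day 15, and Days 15, 17 and 19 are given one level down. Section 6.3 holds carfilzomib only from Grade 3.
- Panobinostat: (2×30 + 3×20)/180 = 120/180 = 67%; 5/6 doses. From a 20 mg start: (2×20 + 3×15)/120 = 85/120 = 71%.
- Carfilzomib: 6/6 doses.
- There is no listed DLT if a reduced dose counts as a required dose. If it does not, panobinostat is 2/6 and the call depends on how the reference to both agents is read.

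**Case 3, cytopenia on Day 8, recovered by Day 15.** Grade 4 thrombocytopenia without bleeding is back to Grade 2 or better at the Day 15 repeat: 7 days, not more than 7. Carfilzomib on Days 8 and 9 is missed.
- Panobinostat: (3×30 + 3×20)/180 = 150/180 = 83%; 6/6 doses.
- Carfilzomib: (2×20 + 2×45)/264 = 130/264 = 49%; 4/6 = 67% of doses.
- If the event is Grade 3, carfilzomib resumes unreduced: (2×20 + 2×56)/264 = 152/264 = 58%, again 4/6 doses.
- If failing either agent suffices, this is a DLT. If both must fall below 75%, it is not.

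**What the 75% rule does catch.** In both situations below, both agents fall under 75%, so the patient has a DLT on either reading.

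| Cytopenia | Panobinostat doses | Carfilzomib doses |
|---|---|---|
| Found Day 8, not recovered by Day 15 | 3/6 | 2/6 |
| First found Day 15 | 3/6 | 4/6 |

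**Leverage on the 3+3 (assumption only).** The chance that a level passes is (1−p)³ + 3p(1−p)⁵, with p the DLT rate. Take p = 0.30 at the full dose and suppose early reductions avert 0%, 25% or 50% of DLTs. The pass chance is then 0.494, 0.654 or 0.814. The documents give no value for the averted share.

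**Level order.** Level 6 has level 5's carfilzomib and less panobinostat, so it is the lower dose. Against level 4 (45 mg/m² with 30 mg), Cycle 1 carfilzomib is 264 versus 2×20 + 4×45 = 220 mg/m² (+20%), and panobinostat is 120 versus 180 mg (−33%). Levels 6 and 4 therefore cannot be ranked. By number, a tolerated level 5 escalates to a lower dose. By the step-down rule, a failed level 5 goes to level 4. A failed level 6 could mean level 3 or level 4.

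**The case against.** Several points limit the concern.

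- **Scope.** The ban sits in the Phase I paragraph and in a subsection of Section 5.2. Section 6 also serves Phase II and later cycles, where nothing conflicts. This stands.
- **Precedence.** Section 5.2.2 is the specific rule for the DLT window and can be read as overriding Tables 5 and 6. That reading is available, though not written. It does not work for Table 7, which is itself a Cycle 1 table.
- **Existing cover.** The 75% rule makes most unrecovered Day 8–15 cytopenias DLTs, and Grade 3 non-hematologic toxicity needing a first-cycle reduction is already listed. Case 3 needs recovery by Day 15, while Section 6.4.6 puts carfilzomib platelet nadirs between Days 8 and 15. It is an edge case. Cases 1 and 2 do not depend on platelet timing.
- **Little left exposed.** Levels 1–4 are complete and only 3–6 patients per parallel level remain. True, but those patients decide whether another dose is expanded.
- **Level 6.** Section 5.3 judges each parallel level on its own tolerability, and level 4 is already a Phase II dose. The ordering gap is therefore minor.

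A reader might infer that Case 2 makes level 5 indistinguishable from level 6. Only the Cycle 1 totals agree: Case 2 gives 30, 30, 0, 20, 20, 20 mg, while level 6 gives 20 mg six times. One constructed patient does not show that the levels cannot be separated.

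**Conclusion.** The conflict is real for Phase I and parallel Phase I patients. It is plain for Table 7 and arguable for Tables 5 and 6. The events left between the rules are drug-related QTcF prolongation in the Table 7 range (unless graded 3 or worse), Grade 3 cytopenia without bleeding or fever that recovers by Day 15, Grade 2 diarrhea or vomiting, and creatinine or bilirubin at 2–3 x ULN. In the worked level 5 cases, panobinostat intensity is 67% to 83% of plan. When carfilzomib alone falls to 4/6, one patient is a DLT or not depending on how one phrase is read.

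The sizes assume that Tables 5–7 are followed as written; Case 2 also assumes that a reduced dose counts as received. Frequency is unknown. Section 1.2.3 reports Grade 3/4 thrombocytopenia in 30 of 38 patients on panobinostat with bortezomib, mostly early, but that is another regimen and shows plausibility only.

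A reader might infer that the absence of DLTs at levels 1–4 is unreliable, or that the chosen dose is too high. The documents do not support either: they report no Cycle 1 reductions at those levels. The point should be corrected, and no sample-size figure changes.

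**What to change.** 1. Amend Sections 5 and 5.2.2, and the matching Synopsis sentence, so that the safety holds and reductions of Tables 5–7 apply in Cycle 1.
2. State that the 75% rule is failed when either agent falls below 75% because of toxicity. This makes Case 3 a DLT. It does not capture Case 2 if a reduced dose counts as received. So, at each dose decision, report by level the number of patients with a Cycle 1 reduction but no DLT, with their dose intensity.
3. Minor: state that level 6 is a panobinostat de-escalation from level 5, judged on its own against at most 1 DLT in 6 and not ranked against level 4. Amend the step-down rule in Section 5.2.1 for the parallel study, so that a failed level 5 may go to level 6 and a failed level 6 ends the parallel escalation. Without that amendment, the present rule sends a failed level 5 to level 4.

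The cost is protocol wording and one table from data already collected. Decisions at levels 5 and 6 become slightly more conservative through the either-agent rule. For levels 1–4 it is a reporting change only.

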### **5.2.3. Definition of Maximum Tolerated Dose (MTD)**

The MTD of carfilzomib and panobinostat when given as a combination therapy will be defined as the highest dose level at which  $\leq 1$  of 6 subjects experiences dose-limiting toxicity (DLT).

#### **When the MTD has been determined:**

When the MTD has been determined, the trial will continue to enroll patients with relapsed/refractory multiple myeloma at the established MTD established during the Phase I portion.

### **5.3. Phase II**

If a dose level in the parallel Phase I study is found to be tolerable, then additional patients will be recruited into an expansion cohort of 30 patients for Phase II for a total of 60 Phase II patients (including 30 patients for dose level 4).. A maximum of up to 80 total patients may be enrolled in this study (including patients from the dose escalation Phase I studies).

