### 5.2.1. Dose Escalation Phase I

The study will follow a standard dose-escalation design (see Table 2). For each cohort, the decision whether to dose-escalate will be made once all subjects have been

enrolled into the cohort and have received one full cycle (28 days) of study drug treatment. The following dose-escalation rules will be used:

- Initially, 3 subjects will be entered into a dose level.
- If 2 or more of the initial subjects experience dose-limiting toxicity (DLT) (see Section 5.2.2), then the MTD (see Section 5.2.3) has been exceeded.
- If none of the 3 subjects initially enrolled into this dose level cohort experiences DLT, then subsequent subjects will be enrolled in the next higher dose level.
- If 1 of the initial subjects experiences DLT, then 3 additional subjects (to a total of 6 subjects) will be enrolled in the dose level.
- If it is found that 1 of the 6 subjects in the dose level encounters DLT, then subsequent subjects will be enrolled into the next higher dose level cohort.
- If it is found that 2 or more of the 6 subjects in a dose level encounter DLT, then the MTD has been exceeded. If  $\geq 2$  of 6 patients have DLT on the first dose level tested (Dose Level 1, Table 2), dose level -1 will be evaluated. If dose level -1 is too toxic ( $\geq 2$  of 6 patients with DLT), the study will continue only after discussion by the study chair and the sponsors.

No intra-patient dose escalation is permitted.

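### The expansion cohorts of 30 patients have no stated trigger that requires a review or pause of enrolment if Cycle 1 dose-limiting toxicities accumulate

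*Combined protocol and SAP*

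**What the plan says.** Section 5.2.2 ties the DLT definition to dose finding: "For the purpose of determining the MTD (see Section 5.2.3), DLT is defined as any of the following", followed by a list of treatment-related Cycle 1 events. Section 5.2.1 sets the limit: "If it is found that 2 or more of the 6 subjects in a dose level encounter DLT, then the MTD has been exceeded". Section 5.2.3 sets the criterion: "The MTD of carfilzomib and panobinostat when given as a combination therapy will be defined as the highest dose level at which" at most 1 of 6 subjects has a DLT. After that, "the trial will continue to enroll patients with relapsed/refractory multiple myeloma at the established MTD established during the Phase I portion".

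For the expansion, Section 5.3 states that "additional patients will be recruited into an expansion cohort of 30 patients for Phase II for a total of 60 Phase II patients", counting the 30 at dose level 4. Section 5 caps an added level at 36 including its Phase I patients, and reports that Phase I produced no DLTs. Section 10.5 plans by-cohort tables of adverse event frequency and severity.

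Controls that do apply in Phase II:
- patient-level holds, reductions and discontinuations (Section 6);
- SAE reports to the sponsor within one business day (11.3.2), to both drug suppliers within 24 hours (11.3.3, 11.3.5), and 7- and 15-day reports of unexpected events to authorities (11.3.6);
- immediate notice to the sponsor of QTc of 480 msec or more (6.2.1);
- dose level assigned by the sponsor at enrolment (Section 5);
- continuing IRB review (12.1).

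Two further texts affect how a DLT would be counted. Section 5.2.2 says "Dose modifications are not permitted during Cycle 1 in any cohort unless the subject experiences a DLT" and lists as a DLT "Patients who are unable to receive 75% of the required doses of both agents secondary to toxicity". Section 6.1 says "Blood counts will be measured on Days 1, 8, and 15 of each cycle, and dose modifications will be based on these blood counts".

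**The concern.** A 3-to-6-patient cohort gives little information on a level's DLT rate. Most of that information arrives in the 30-patient expansion, where Sections 5, 5.3, 6, 10 and 11 require no DLT count, no pooled toxicity review and no enrolment pause. Followed as written, an expansion could fill while its running DLT proportion stayed at or above the 2-of-6 proportion that Phase I treats as too high. The excess would be visible in the 10.5 tables, but no text obliges anyone to act on it while patients are still entering.

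SAE reporting is not a full substitute, because it works event by event. Some DLTs need not be SAEs, such as grade 4 neutropenia beyond 7 days or missed doses under the 75% item. What is at stake is avoidable toxicity in up to 30 new patients per level.

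**Working it through.** **Expansion size (the plan's own figure).** Section 10.1: 18% against 36%, one-sided alpha 0.10, n = 27. The exact binomial rule of at least 8 responses in 27 gives alpha 0.098 and power 0.812. Adding 10%: 27 × 1.10 = 29.7, so 30. The size reproduces.

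**Inputs.** Limits of 2 or more of 6 (5.2.1) and at most 1 of 6 (5.2.3); 30 patients per expansion (5.3). The true DLT rates p are assumptions, because the documents give no expected rate. Write q = 1 − p.

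**Strength of the Phase I gate.**
- Passing the 5.2.1 step: q³ + 3pq² × q³.
- Meeting the 5.2.3 criterion: q⁶ + 6pq⁵.
- One-sided 95% upper limit after no DLTs in n: 1 − 0.05^(1/n). This is 63% for 0 of 3 and 39% for 0 of 6.

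The number treated at level 4 is not stated. The 5.2.1 rules go to six only after a DLT, so three is possible.

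**Boundary examined.** Pause at 3/6, 5/12, 7/18 or 9/24. Calculate P(n,x) = P(n−1,x)q + P(n−1,x−1)p up to n = 30, and remove the paths at or above the boundary at each look. At p = 0.40 the first look removes 1 − (0.047 + 0.187 + 0.311) ≈ 0.456, and the later looks remove 0.177, 0.096 and 0.061, for a total of 0.790. If every pause were final and enrolment waited at each look, mean enrolment would be 6(0.456) + 12(0.177) + 18(0.096) + 24(0.061) + 30(0.210) = 14.35, and expected DLT patients 0.40 × 14.35 = 5.7.

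| True rate (assumed) | 25% | 1/3 | 40% | 50% |
|---|---|---|---|---|
| Passes 5.2.1 step | 0.60 | 0.43 | 0.31 | 0.17 |
| Meets 5.2.3 criterion | 0.53 | 0.35 | 0.23 | 0.11 |
| Expected DLT patients, no rule (30p) | 7.5 | 10 | 12 | 15 |
| Pause probability | 0.29 | 0.58 | 0.79 | 0.96 |
| Mean enrolment with rule | 24.2 | 18.7 | 14.4 | 9.7 |
| Expected DLT patients with rule | 6.1 | 6.2 | 5.7 | 4.9 |
| Spared × 5.2.3 pass chance | 0.8 | 1.3 | 1.5 | 1.1 |

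The last row at 40%, for example, is 0.233 × (12 − 5.74) = 1.46. At true rates of 10% and 1/6 the pause probabilities are 0.02 and 0.09. With two cohorts at 1/6, the chance that at least one pauses is 1 − (1 − 0.087)² = 0.17.

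**Level 4.** It had no DLTs, so the 1-of-6 weights are not its own. Weighting by q⁶ (0 of 6) gives about 0.2 to 0.3 spared; at 40%, 0.6⁶ × 6.26 = 0.29. Weighting by q³ (0 of 3) gives about 0.6 to 1.4.

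**Counting trap.** Take grade 3 thrombocytopenia without bleeding on Day 15. It is not itself a DLT. A Table 5 hold with weekly repeat labs runs to Day 22. Panobinostat Days 15, 17 and 19 are lost (3/6 = 50% given), and carfilzomib Days 15 and 16 (4/6 = 67% given). Both are under 75%, so the hold alone would count as a DLT. If such holds added 5 or 10 points (assumed) to a true rate of 1/6, the false-pause chance would rise from 0.09 to 0.19 or 0.34.

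**The case against.** The strongest reply is that oversight exists and the trade-off belongs to the sponsor. The sponsor sees every SAE within a business day, assigns each patient's dose level and can stop a level at any time. A cohort review might also sit in the Safety Monitoring Plan, which was not available; the protocol cites it only for SAE reporting. This stands. A reader might infer that the expansions run without safety oversight, and the documents do not support that. What is missing is a pre-stated trigger in the protocol.

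Second, the boundary is looser than the Phase I limit. It lets 2/6, 4/12, 6/18 and 8/24 continue, misses a true rate of 25% with probability 0.71 and misses 33% with probability 0.42. This also stands, so the rule should not be presented as enforcing the Phase I limit. A boundary at the Phase I proportion (2/6, 4/12, 6/18, 8/24) would pause 30% of the time at a true rate of 1/6.

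Third, the gain is modest: about 1 to 1.5 DLT patients per cohort under favourable assumptions, and less for level 4. That bears on the priority of the change, but the cost is small too.

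Fourth, carrying the 5.2.2 replacement rule into the expansion would conflict with Section 3.3, which does not replace discontinued patients. The fix below avoids that.

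**Conclusion.** The gap is real but limited. The protocol carries the expansions to 30 patients per level without a cohort-level trigger for review or pause, after a Phase I gate that a level with a true DLT rate of 33% or 40% meets with probability 0.35 or 0.23. Adding a trigger is a cheap improvement to patient protection. It does not touch the response-rate analysis.

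The size rests on assumed true rates, and the best-case savings also assume that pauses are final and that enrolment waits at each look. If 2, 4 or 6 patients (assumed) enter while a block completes Cycle 1, mean enrolment at the pause at a 40% rate rises from 10.2 to 12.2, 14.2 or 16.2, so fewer are spared.

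A reader might also infer that dose level 4 is too toxic. Nothing in the documents shows this. No DLTs were seen there, and the 63% and 39% upper limits only describe how little 3 or 6 patients can exclude.

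**What to change.** In Section 5.3:

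1. Count Cycle 1 DLTs (5.2.2 definition) in each expansion cohort in enrolment order. A patient is evaluable on completing Cycle 1 or on having a DLT, whichever comes first. Others are left out of the count and not replaced, in line with 3.3 and the 10% allowance in 10.1.
2. State whether Table 5 holds are allowed in expansion Cycle 1. If they are, doses missed through holds for events that are not DLTs do not count under the 75% item.
3. The study chair and sponsor review the count after every 6 evaluable patients and pause enrolment at that level for review at 3/6, 5/12, 7/18 or 9/24. Enrolment continues while a block completes Cycle 1 unless a boundary is met.
4. Describe the rule as a backstop against clearly excessive toxicity, looser than the Phase I limit, and print its pause probabilities: 0.02, 0.09, 0.29, 0.58, 0.79 and 0.96 at true rates of 10%, 1/6, 25%, 33%, 40% and 50%.

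In Section 10.5, report the DLT rate with an exact interval for each expanded level.

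The cost is protocol wording, up to four short reviews per cohort by existing staff on data already collected, and a 9% chance per cohort of an unnecessary temporary pause at a true rate of 1/6. No new committee is needed.
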